7.4.2 Analysis of Secondary Efficacy Endpoint

CR rate, best response rate, duration of remission, OS and EFS will be summarized using descriptive statistics. The CR rate, best response rate with the corresponding 95% confidence interval will be reported. The survival curve and the median time for time to event variables will be estimated using the Kaplan-Meier method and will be reported along with the corresponding 95% confidence interval.

The SAS code used to produce median from Kaplan-Meier estimates and corresponding 95% CI will be similar to that shown below:

```
proc lifetest data=adtte plots=(s) outsurv=surv;  
time survtime*censor(0);
```

run;

7.4.3 Analysis of Exploratory Efficacy Endpoint

- Evaluate efficacy of gilteritinib given in combination with atezolizumab in terms of minimal residual disease (MRD). MRD analysis will be conducted on the BMAS. MRD will be assessed in relation to the following efficacy variables:
 - CR rate
 - CRc rate
 - EFS
 - Duration of remission
 - OS
- Evaluate potential genomic, proteomic and/or other biomarkers that may correlate with treatment outcome
- Evaluate pharmacodynamic biomarkers of treatment effect
- Evaluate immune cell populations and AML blasts by immunophenotyping in relation to treatment effects

7.5 Analysis of Safety

All analysis of safety will be performed on the SAF, unless specified otherwise.

7.5.1 Adverse Events

Any adverse event (AE) recorded on treatment including within 30 days from the last study treatment will be classified as treatment-emergent AE (TEAE) and will be summarized.

Summaries and listings of TEAEs and Serious TEAEs include SAEs upgraded by the Sponsor based on review of the Sponsor's list of Always Serious terms if any upgrade was done.

The number and percent of subjects experiencing one or more AE(s) will be summarized by SOC and PT using MedDRA and will be graded according to the National Cancer Institute Common Terminology Criteria for Adverse Events (NCI-CTCAE) version 5.0. The number and percentage of subjects with at least one grade 3 or higher AE will also be summarized by SOC and PT.

An overview table will include the following details:

- Number and percentage of subjects with TEAEs,
- Number and percentage of subjects with causally drug related TEAEs,
- Number and percentage of subjects with serious TEAEs and Astellas upgraded serious TEAE,
- Number and percentage of subjects with serious drug related TEAEs and Astellas upgraded serious drug related TEAE,
- Number and percentage of subjects with TEAEs leading to permanent discontinuation of study drug,
- Number and percentage of subjects with drug related TEAEs leading to permanent discontinuation of study drug,

- Number of deaths, and
- Number and percentage of subjects with grade 3 or higher TEAEs.

The number and percentage of subjects with TEAEs, as classified by SOC and PT will be summarized by period, cohort and dose level. Summaries will be provided for:

- TEAEs
- Drug related TEAEs,
- Serious TEAEs and Astellas upgraded serious TEAE,
- Drug related serious TEAEs and drug related Astellas upgraded serious TEAE,
- TEAEs leading to permanent discontinuation of study drug,
- Drug related TEAEs leading to permanent discontinuation of study drug,
- TEAEs excluding serious adverse events that equal to or exceed a threshold of 5% in any dose level,
- Common TEAEs that equal to or exceed a threshold of 5% in any dose level, and
- Grade 3 or higher TEAEs.

The number and percentage of subjects with TEAEs, as classified by PT only, will be summarized.

AE summary tables will include subject counts as opposed to AE counts. If a subject experiences more than one episode of a particular AE, the subject will be counted only once for that AE. If a subject has more than one AE that code to the same preferred term, the subject will be counted only once for that preferred term. Similarly, if a subject has more than one AE within a SOC, the subject will be counted only once in that SOC.

The number and percentage of subjects with TEAEs, as classified by SOC and PT will also be summarized by NCI-CTCAE severity grade and by relationship to study drug. In the subject count, if a subject has multiple TEAEs with the same SOC or PT, but with differing severity grade or relationship, then the subject will be counted only once with the worst severity grade and highest degree of relationship, however, if any of the severity grade or relationship values are missing then the subject will be counted only once with missing severity grade or relationship. Drug related TEAEs will be presented in a similar way by severity grade only.

The number and percentage of subjects with adverse events of special safety interest (AESIs) for Atezolizumab will be summarized by PT. See [Appendix 12.7 Adverse Events of Special Interest (AESI) for Atezolizumab] for further details.

All summaries of AEs will include only TEAEs unless otherwise stated. All AEs, deaths, SAEs and withdrawals due to adverse events will be displayed in listings.

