5.1.4 Previous and Concomitant Treatment (Medication and Non-Medication Therapy)

All medications and concomitant treatments administered from 28 days prior to cycle 1/day 1 through the EOT Visit must be recorded in the electronic case report form (eCRF).

Concomitant medications should be collected for reported or ongoing AE/serious adverse events (SAEs) through 30 days after the last dose of study drug for subjects who have discontinued treatment. For subjects who undergo HSCT, concomitant medications should be collected for reported or ongoing AE/SAEs through start of conditioning treatment or 30 days after the last dose of study drug, whichever comes first. Treatment with concomitant drugs that are strong inducers of CYP3A are prohibited. Treatment with concomitant drugs that are strong inhibitors or inducers of P-gp and concomitant drugs that target serotonin 5HT_{2B}R or sigma nonspecific receptor are to be avoided with the exception of drugs that are considered absolutely essential for the care of the subject. Treatment with concomitant drugs that are strong inhibitors of CYP3A should be avoided with the exception of antibiotics, antifungals and antivirals that are used as standard of care to prevent or treat infections. If CYP3A inhibitors are used concomitantly, subjects should be closely monitored for AEs.

Precaution should be used in use of gilteritinib with concomitant drugs that are known to prolong QT or QTc intervals.

Precaution should be used in use of gilteritinib with concomitant drugs that are substrates of BCRP, since the transporter has been shown to be inhibited by gilteritinib in in vitro studies.

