5.5 Adverse Events and Other Safety Aspects

5.5.1 Definition of Adverse Events

An AE is any untoward medical occurrence in a subject administered a study drug, and which does not necessarily have to have a causal relationship with this treatment. An AE can therefore be any unfavorable and unintended sign (including an abnormal laboratory finding), symptom or disease (new or exacerbated) temporally associated with the use of a medicinal product whether or not considered related to the medicinal product.

In order to identify any events that may be associated with study procedures and could lead to a change in the conduct of the study, Astellas collects AEs even if the subject has not received study drug treatment. AE collection begins after the signing of the ICF and will be collected until 30 days after the last dose of study drug or the subject is determined to be a screen failure.

Care will be taken not to introduce bias when detecting AEs and/or SAEs. Open-ended and non-leading verbal questioning of the subject is the preferred method to inquire about AE occurrences.

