- Subject receives any antileukemic therapy (including HSCT) other than the assigned treatment, with the exception of hydroxyurea up to 5 g daily for up to 2 weeks, prophylactic intrathecal chemotherapy or cranial irradiation.
- Subject has not achieved a PR or CRc, and in the opinion of the investigator, is no longer deriving clinical benefit after 6 cycles of therapy.
- Investigator/subinvestigator determines that the continuation of the study treatment will be detrimental to the subject.
- Subject is lost to follow-up despite reasonable efforts by the investigator to locate the subject.
- Female subject becomes pregnant.
- Death
- Subject is receiving gilteritinib, atezolizumab, or the combination of gilteritinib + atezolizumab and has progressive disease, recurrence under treatment, or no response, and in the opinion of the investigator the subject is no longer deriving clinical benefit.

Discontinuation criteria from long term follow-up for individual subjects:

- Subject declines further study participation (i.e., withdraws consent)
- Subject is lost to follow-up despite reasonable efforts by the investigator to locate the subject.
- More than 3 years has passed from the EOT Visit.
- Death

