7.5.1 Adverse Events

All AEs recorded on treatment including within 30 days from the last study treatment will be summarized. AEs will be categorized by SOC and PT using the MedDRA dictionary and will be graded according to the NCI CTCAE version 5.0.

The number and percent of subjects experiencing 1 or more AE(s) will be summarized by treatment group, SOC and PT. The number and percentage of subjects with at least one grade 3 or higher AE will be summarized by treatment group, SOC and PT.

Distribution of the maximum severity (grade) and treatment-related AEs will be summarized by treatment group, SOC and PT. Distribution of SAEs, discontinuations due to AE and deaths on study will be presented for each treatment group.

Additional summary tables will be generated for the following population subsets: subjects with SAEs including deaths, subjects who discontinue due to AEs and investigator-attributed relationship to study drug for AEs and SAEs.

All summaries of AEs will include only TEAEs unless otherwise stated. Listings of AEs, SAEs, deaths and withdrawals due to AEs will be presented.

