6.2.4 Adverse Events

Any adverse event (AE) recorded on treatment including within 30 days from the last study treatment will be classified as treatment-emergent AE (TEAE) and will be summarized.

A drug-related TEAE is defined as any TEAE with at least possible relationship (possibly or probably related) to study treatment as assessed by the investigator or with missing assessment of the causal relationship

Serious adverse events (SAEs) include adverse events that are flagged as serious by the investigator or sponsor on eCRF, or upgraded by the Sponsor based on review of the Sponsor's list of Always Serious term.

Adverse events of special safety interest (AESI) are defined in the Safety Review Plan for ASP2215.

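### The flat 30-day TEAE window has no split at transplant conditioning or new antileukemic therapy, so later therapy's toxicity can enter the all-cause AE tables; a supplementary tabulation is needed

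*SAP*

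**What the plan says.** SAP 7.5.1 sets the window: "Any adverse event (AE) recorded on treatment including within 30 days from the last study treatment will be classified as treatment-emergent AE (TEAE". SAP 6.2.4 repeats it ("within 30 days from the last study treatment will be classified as treatment-emergent AE (TEAE"). Protocol 7.5.1 summarises the same period: "All AEs recorded on treatment including within 30 days from the last study treatment will be summarized". Protocol 5.5.1 collects over it too, since AEs "will be collected until 30 days after the last dose of study drug or the subject is determined to be a screen failure". None of these sections ends the window, or flags events, when a subject begins another leukemia treatment. SAP 7.5.1 also limits its AE summaries to TEAEs unless it says otherwise, so this one definition controls nearly every AE table.

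Other treatment after the last dose is foreseen. Protocol 6.1 lists as a reason for withdrawal from study treatment: "Subject receives any antileukemic therapy (including HSCT) other than the assigned treatment". Limited hydroxyurea, prophylactic intrathecal chemotherapy and cranial irradiation are excepted.

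Protocol 5.1.4 already treats conditioning as a boundary for medication records. It says: "For subjects who undergo HSCT, concomitant medications should be collected for reported or ongoing AE/SAEs through start of conditioning treatment", or to day 30 if that comes first. For other subjects who stop treatment, medications linked to AEs are collected "through 30 days after the last dose of study drug for subjects who have discontinued treatment".

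**The concern.** Conditioning and salvage regimens cause toxicity of their own. If either starts within 30 days of the last dose, an event it causes is a TEAE under the SAP and is counted beside events that arose on the combination alone. With no control arm, a reader of the all-cause tables cannot tell how much of a rate belongs to the later therapy.

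The subjects concerned are not a random subset. They include those who did well enough to go to transplant and those who failed and moved to another treatment. Safety and tolerability is a primary objective (protocol 2.1.1), and AEs are part of a primary endpoint (protocol 2.3.1, SAP 6.2).

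**Working it through.** The plan states no figure on this point, so there is none to reproduce. The check compares sections, then does simple arithmetic.

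**Where the post-treatment periods end**
- AE collection (protocol 5.5.1): 30 days after last dose for everyone.
- TEAE classification (SAP 6.2.4 and 7.5.1, protocol 7.5.1): the same 30 days.
- Death reporting (protocol 5.5.1.3): every death to day 30 is an SAE, whatever its cause.
- AE-related concomitant medications (protocol 5.1.4): day 30, or start of conditioning if sooner for HSCT subjects. The same section requires all medications to be recorded through the EOT visit, so the gap is plain only after that visit.
- Remission duration (protocol 5.3.3.4, SAP 6.1.4): censored at allogeneic HSCT.
- Subsequent antileukemic treatment including HSCT (protocol 5.3.3.1 and Table 1): collected for all subjects from the 30-day contact onward.

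HSCT is thus recognised in the medication and remission-duration rules but not in the TEAE window. The information needed for a split is largely collected, but the SAP does not use it for safety.

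**Which outputs are exposed**
- All-cause TEAEs, grade 3 or higher TEAEs, serious TEAEs and deaths: exposed, because entry depends on timing alone.
- Drug-related tables: exposed only if the investigator misjudges the event as related or leaves causality blank, since SAP 6.2.4 counts missing causality as related.
- DLTs (SAP 6.2.1): largely unexposed, because the event must be possibly or probably related and fall in cycle 1, days 1 to 28.

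**Effect of one subject.** SAP 7.5.1 counts a subject once per preferred term, so a row rises only when the subject's first qualifying event comes after the switch.
- Full phase 2: 1/49 = 2.0 percentage points.
- Phase 2 stopped after stage 1: 1/22 = 4.5 points.
- SAP 7.5.1 also has tables with a 5% threshold. With 49 subjects, 2/49 = 4.1% is below it and 3/49 = 6.1% is above it.

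**Illustration under assumptions.** Let h be the share starting other therapy inside the window, b the event rate on the combination alone, and c the event risk from the other therapy, acting independently. The tabulated rate is b + h(1 − b)c. The documents give none of these, so I assume h from 10% to 30% and c from 30% to 70%.
- b = 5%: from 0.05 + 0.1 × 0.95 × 0.3 = 7.85% to 0.05 + 0.3 × 0.95 × 0.7 = 24.95%. That is 1.4 to 9.8 extra subjects of 49.
- b = 20%: from 0.20 + 0.1 × 0.8 × 0.3 = 22.4% to 0.20 + 0.3 × 0.8 × 0.7 = 36.8%. That is 1.2 to 8.2 extra subjects.

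The width of these ranges shows that the effect cannot be sized from the documents. They are not estimates.

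**The case against.** The flat window has a good defence. TEAE is a timing label, and attribution is handled elsewhere: SAP 7.5.1 provides drug-related tables and a breakdown by relationship, and protocol 5.5.3 tells investigators to weigh alternative explanations, including other drugs. The window matches AE collection, AESI reporting and the day-30 death rule. Protocol 1.2.3.2 gives gilteritinib a half-life of 45 to 159 hours. Five half-lives are 225 to 795 hours, about 9 to 33 days, so a subject who switches inside the window may still carry study drug. Truncation can then drop real combination toxicity. All of this stands, and it is why the 30-day definition should not be replaced.

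Some rows also have little room to rise. Protocol 1.3.1 reports any-TEAE rates of 98.8% and 100% (246/246) in two gilteritinib studies and lists febrile neutropenia among the most frequent TEAEs, so many subjects may already be counted. This limits the effect on common rows but not on less frequent serious or fatal events.

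A reader might infer more than the documents support:
- *That the plan attributes other treatments' toxicity to the combination.* It does not, since attribution has its own tables.
- *That the treatments responsible go unrecorded.* Only concomitant-medication collection stops at conditioning, and only for HSCT subjects. HSCT and later therapy are recorded as subsequent treatment.
- *That rates will be inflated by some known amount, such as 10 points.* That would need five affected subjects (5/49 = 10.2%), and nothing in the documents supports that count.

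**Conclusion.** The point holds as a reporting gap. All-cause summaries over the 30-day window can mix toxicity arising on the combination with toxicity arising after other therapy began, and no planned table lets a reader separate them. The gap matters because the trial has one arm and safety is a primary objective. It does not undermine the drug-related tables, except through misjudged or missing causality, or to any large extent first-cycle DLT decisions.

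The size is unknown. What can be stated is 2.0 points per affected subject in a full phase 2. This assumes 49 treated subjects and that the subject had no qualifying event before the switch.

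**What to change.** Keep the 30-day TEAE definition and its tables as primary. In SAP 7.5.1 add two supportive items:

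1. A supplementary set of the all-cause, grade 3 or higher, serious and fatal TEAE summaries. These stop at the earlier of 30 days after last dose and the day before HSCT conditioning or new antileukemic therapy.
2. A separate table of the remaining events to day 30, labelled as after start of subsequent therapy and including events of any causality. Keeping all causalities together avoids mixing timing with attribution. State the number of subjects who switched within 30 days, which supplies the missing rate.

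Define new antileukemic therapy as treatment that triggers withdrawal under protocol 6.1, so that its permitted exceptions do not start the cut.

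The dates should largely exist already. Conditioning start is needed for protocol 5.1.4, subsequent treatment is collected under protocol 5.3.3.1, and the HSCT date is needed for censoring in SAP 6.1.4. Confirm that the eCRF holds start dates for conditioning and for non-transplant therapy.

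Protocol 5.1.2.1 words its resumption rule around time off treatment for HSCT, while 6.1 withdraws subjects who receive HSCT. These sections must be reconciled, because resumption would put the whole transplant period before the last dose and so inside the TEAE window.

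The cost is SAP wording and one more set of tables. The truncated version may omit some delayed study-drug toxicity, so it is supportive only.

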5.5.4 Criteria for Defining the Severity of an Adverse Event

AEs, including abnormal clinical laboratory values, will be graded using the National Cancer Institute Common Terminology Criteria for Adverse Event (NCI-CTCAE) guidelines (version 5.0). The items that are not stipulated in the NCI-CTCAE version 5.0 will be assessed according to the criteria below and entered into the eCRF:

Grade	Assessment Standard
1-Mild	Asymptomatic or mild symptoms, clinical or diagnostic observations noted; intervention not indicated.
2-Moderate	Local or noninvasive intervention indicated.
3-Severe	Medically significant but not immediately life threatening, hospitalization or prolonged hospitalization.
4-Life Threatening	Life threatening consequences, urgent intervention indicated
5-Death	Death related to AE

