7.11 Handling of Missing Data, Outliers, Visit Windows, and Other Information

Imputation methods for missing data, if applicable, and the definitions for windows to be used for analyses by visit will be outlined in the SAP.

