7 STATISTICAL METHODOLOGY

7.1 General Considerations

For continuous variables, descriptive statistics will include the number of subjects (n), mean, standard deviation, median, minimum and maximum. When needed, the use of other percentiles (e.g., 10%, 25%, 75% and 90%) will be mentioned in the relevant section. In addition, for continuous PK parameters, the coefficient of variation will be calculated and for C_{max} and AUC the geometric mean will also be calculated. Frequencies and percentages will be displayed for categorical data. Percentages by categories will be based on the number of subjects with no missing data, i.e. will add up to 100%. Kaplan-Meier survival curves will be displayed for time-to-event variables and median survival time will be estimated with 2-sided 95% confidence interval (CI).

Safety analysis and other summaries based on SAF will be presented by actual treatment received. Pharmacokinetic summaries based on will be presented by actual treatment received. For subjects with dose change, actual treatment refers to the first dose received before dose change.

All data processing, summarization, and analyses will be performed using SAS[®] Version 9.3 or higher on Unix. Specifications for table, figure, and data listing formats can be found in the TLF specifications for this study.

Baseline is defined as the last available measurement prior to the first dose of study drug. Unless otherwise specified, all summaries and analysis will be presented by phase.

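### One ungraded record overrides a known worst grade in the SAP's by-grade TEAE tables, so they may not show maximum severity

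*SAP*

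**What the plan says.** Protocol 7.5.1 sets the target: "Distribution of the maximum severity (grade) and treatment-related AEs will be summarized by treatment group, SOC and PT". It gives no rule for a missing grade. Protocol 7.11 leaves missing data to the SAP: "Imputation methods for missing data, if applicable, and the definitions for windows to be used for analyses by visit will be outlined in the SAP".

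SAP 7.5.1 starts from the same idea. A subject with several TEAEs of differing grade in one SOC or PT is handled so that "then the subject will be counted only once with the worst severity grade and highest degree of relationship". The same sentence then makes an exception: "if any of the severity grade or relationship values are missing then the subject will be counted only once with missing severity grade" (or, correspondingly, missing relationship). A known grade 3, 4 or 5 is not protected from it. The rule carries over to the related events: "Drug related TEAEs will be presented in a similar way by severity grade only".

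Three other provisions bear on the point:

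- SAP 7.5.1 plans a separate high-grade summary: "The number and percentage of subjects with at least one grade 3 or higher AE will also be summarized by SOC and PT".
- SAP 7.1 has a general rule on percentages: "Percentages by categories will be based on the number of subjects with no missing data, i.e. will add up to 100" percent.
- SAP 7.11.1, the missing-data section, imputes dates. It has no rule for grade.

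**The concern.** A table of maximum severity should place each subject at the worst grade known to have occurred. Under the SAP rule, an extra record that carries no grade information removes a grade that is known. Counts in the grade 3, 4 and 5 rows can then be too low.

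Two tables from the same SAP section can also disagree. A subject with a grade 4 record and an ungraded record of the same PT is in the grade 3 or higher summary but in none of the grade 3 to 5 rows of the by-grade table.

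The drug-related table is the most exposed, because SAP 7.5.1 lists no drug-related grade 3 or higher summary to check it against. The drug-related serious table covers serious events only, so a non-serious drug-related grade 3 event could be missing from every drug-related count restricted to high grades. SAP 6.2.4 also classes a TEAE with missing causality as drug-related. If such a record lacks a grade too, it can hide a known grade in that table.

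Adverse events are part of a primary endpoint, so these tables will be read closely.

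**Working it through.** The plan attaches no figure to this rule, so there is none to reproduce. The check applies the rule to example subjects and then gives a scale under stated assumptions.

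**Step 1. Apply the rule.** Each row is one subject's set of records within one SOC or PT.

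| Records | Row under SAP 7.5.1 | Row at worst non-missing grade | In grade 3 or higher summary |
|---|---|---|---|
| 5, missing | missing | 5 | yes |
| 4, missing | missing | 4 | yes |
| 3, 1, missing | missing | 3 | yes |
| 3, 1 | 3 | 3 | yes |
| 1, missing | missing | 1 | no |
| missing only | missing | missing | no |

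The first three rows show the problem: a subject known to have had a grade 3 or higher event appears in no grade 3 to 5 row.

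**Step 2. Compare with the protocol.** With {5, missing} the maximum is 5 whatever the ungraded record was, so a missing entry is wrong. With {3, missing} or {4, missing} the true maximum is not known exactly, but it is at least 3 or 4. The SAP rule discards that bound. Because Protocol 7.11 delegates missing data to the SAP, a definite conflict with Protocol 7.5.1 arises only in the grade 5 case.

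**Step 3. Look for a repair elsewhere.** SAP 7.11.1 does not address grade. SAP 7.1 may make matters worse. If its rule on percentages applies to these tables, subjects moved to missing also leave the denominator. The SAP does not say whether it applies, so no shift in percentage points is computed here.

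**Step 4. Scale.** Let m be the number of records the subject has in the category, one of which carries the known worst grade. Let q be the probability that any other record is ungraded, independently of the rest. Then

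P(known worst grade hidden) = 1 − (1 − q)^(m − 1)

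For example, with q = 1% and m = 10: 1 − 0.99^9 = 0.0865. The documents give neither q nor m; both are assumptions.

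| m | q = 0 | q = 0.5% | q = 1% | q = 2% |
|---|---|---|---|---|
| 2 | 0 | 0.5% | 1.0% | 2.0% |
| 5 | 0 | 2.0% | 3.9% | 7.8% |
| 10 | 0 | 4.4% | 8.6% | 16.6% |

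Two records is a plausible figure for one PT. Ten is possible only for a busy SOC. As a count, with m = 2 and q = 1%, even if all 61 planned subjects had two records of the same PT, 61 × 0.01 = 0.61 subjects would be expected to move to missing.

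**The case against.** The best defense is that, for a known grade 1 to 4 beside an ungraded record, the true maximum is unknown. The SAP reports that as missing; the alternative reports a lower bound. Neither gives the true maximum, and the protocol lets the SAP choose. This stands as far as it goes, and is why the conflict is called certain only for grade 5. It does not justify discarding the bound, since a footnote can disclose the uncertainty and keep it.

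The grade 5 case is also the best protected. Deaths are counted in the overview table and listed, and fatal events stay in the serious and the grade 3 or higher tables. The subject is relabeled, not dropped, so a displayed missing row limits how far any grade row can be understated. Laboratory toxicities have their own CTCAE tables in SAP 7.5.2, including shifts to the worst post-baseline grade. All of this is true and reduces the consequence, but none of it makes the by-grade table correct.

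The trigger may be rare. Protocol 5.5.4 requires grading ("AEs, including abnormal clinical laboratory values, will be graded using the National Cancer Institute Common Terminology Criteria"), with a fallback scale for events the criteria do not cover. Protocol 8.1 requires complete eCRF data, and SAP section 1 plans a data review before hard lock. This stands too: the effect may be zero, and the percentages above rest on assumed rates. But since the SAP has written a rule for this case, the rule should give the right row when it is used.

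On the denominator, SAP 7.1 may never have been meant for AE incidence tables. That is a fair reading, and the point here is only that the text does not settle it.

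Finally, the same sentence sends missing relationship to a missing category, while SAP 6.2.4 treats missing causality as drug-related. That is a real difference between two sections, but a separate matter; this point concerns grade only.

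**Conclusion.** The concern holds. As written, SAP 7.5.1 lets one ungraded record displace a known worst grade at SOC or PT level, in both the all-TEAE and the drug-related by-grade tables, and no other section corrects it. The row is plainly wrong for a known grade 5. For a known grade 3 or 4 a lower bound is lost and the table can contradict the grade 3 or higher summary.

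The impact is modest and confined to descriptive tables. The events remain in the grade 3 or higher summary, in the listings and, where applicable, in the serious tables and the death count. How many subjects are affected depends on a rate of ungraded records that the documents do not state, and on how such records cluster within subjects. Confidence is high in the reading of the rule, not in any particular size of effect. The change should be made, because the rule is easy to put right before lock.

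**What to change.** In SAP 7.5.1, for the all-TEAE and drug-related by-grade tables:

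- Count each subject once at the worst non-missing grade within the SOC or PT, and use the missing category only when no record there is graded.
- State that the denominator is all subjects in the analysis set, so that the general rule in SAP 7.1 does not apply to these tables.
- Footnote the number of subjects with any ungraded record in that SOC or PT.

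The small downside is that a subject with a grade 1 and an ungraded record will be shown as grade 1; the footnote discloses this. The relationship rule is left as it is under this point.

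The cost is two sentences and one footnote in the SAP, plus a small programming change before database lock. No new data are needed.
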